12 lead ECG ^f	X	X/X	X	X	X/X		X	X				X	6-weekly normal ECGs ^t	-/X	X	
Vital signs including weight and height (height at screening only) ^g	X	X			X	X	X	X	X	X	X	X	2-weekly	x/X	Х	
ECOG PSh	X	X	X	X	X		X	X		X	X	X	2-weekly	x/X	X	
Enrollment (if eligible)i	X															
Hematology/ hemostaseology ^j	X	X	X	Х	Х	Х	Х	X		X	Х	Х	2-weekly	x/X	X	
Core serum chemistryk		X	X	X		X	X			X	X		2-weekly			
Full serum chemistryk	X				X			X				X	6-weekly	x/X	X	
Urinalysis ^l	X				X			X				X	6-weekly ^t	x/X	X	
β-HCG pregnancy test (if applicable) ^m	X	X					Х			X		X	4-weekly	-/X	X	
FSH (if applicable)	X															
CCI																I I
Documentation of AEsw	X	X	X	X	X	X	X	X	X	X	X	X	2-weekly	x/Xw	Xw	
Documentation of concomitant medications, and procedures	Х	X	Х	Х	X	Х	X	X	X	Х	Х	X	2-weekly	x/X	Х	X
ACTH, ANA, and RF	X															

Table 2	Schedule	of A	Asses	sme	nts:	Exp	ansio	on Pa	ırt							
	Screening Assessments								ent Part days) ^a					Discontinuation/ End-of-Treatment Visits ^w	Safety Follow-up Visit ^w	Long-Term Follow-up ^b
		V1x V2 V3 V4 V5 V6 V7 V7 V8 V9 V10 W1 W1 W2 W3 W4 W5 W7 W7 W9 W11 W13														
		W1	W1	W2	W3	W4	W5	W 7	W 7	W9	W11	W13		Up to 7/28 Days (+/- 5 days) after	10 Weeks	
	Day -28 to	D1												Decision of	(+/- 2 weeks)	
Measure	First Treatment		Progressio										Until Progression	Discontinuation/ Last Treatment ^{c, d}	after Last Treatment	Every 12 weeks (+/- 2 weeks)
Free T4 and TSH	X		X X X 6-weekly										6-weekly	-/X	X	
EBV testing ^p	X															
PK sampling		See Table 3														
ADA sampling		See Table 3														
Soluble factors ^{cc}		See Table 3 See Table 3														
TGFβ ^{cc}										5	See Ta	ble 3				
Tumor tissue or archived surgical specimen / paired biopsy ^{cc}										S	See Ta	ble 3				
CCI																
Pretreatment and IMP administration ^r	2	X		2	X	X		X		X	X	X	2-weekly			
Expansion: GC, ESCC a	nd BTC ^y	C y														
Patient-reported Outcomes (PGIS and EORTC QLQ-C30, QLQ-STO22, ² QLQ-OES18, ^{2a} QLQ-BIL21, ^{bb} and QLQ-HCC18, ^{bb})	X										2-weekly up to Week 25	x/X	X			

Table 2	Schedule	of A	Asses	ssme	nts:	Expa	ansid	n Pa	art							
	Screening Assessments								ent Part days) ^a					Discontinuation/ End-of-Treatment Visits w	Safety Follow-up Visit ^w	Long-Term Follow-up ^b
		V1x	V2	V3	V4	V5	V6	V7	V7	V8	V9	V10				
		W1	W1	W2	W3	W4	W5	W7	W7	W9	W11	W13		Up to 7/28 Days (+/- 5 days) after	10 Weeks	
Measure	Day -28 to First Treatment	D1	D2 ^{cc}	D8cc	D15	D22 ^{cc}	D29	D43	D43- 50 ^{cc}	D57	D71	D85	Until Progression	` '	(+/- 2 weeks)	Every 12 weeks (+/- 2 weeks)

ACTH=adrenocorticotropic hormone; ADA=anti-drug antibody; AE=adverse events; ANA=anti-nuclear antibody; β-HCG=β-human chorionic gonadotropin; CT=computer tomography; DLT=dose-limiting toxicity; EBV=epstein barr virus; ECG=electrocardiogram; ECOG PS=Eastern Cooperative Oncology Group Performance Status; EORTC QLQ-C30=European Organisation for Research and Treatment of Cancer Quality of Life Questionnaire Core instrument; EORTC QLQ-STO22=stomach cancer module; EORTC QLQ-OES18=esophageal cancer module; EORTC QLQ-BIL21=cholangiocarcinoma and gallbladder cancer module; EORTC QLQ-HCC18= hepatocellular carcinoma module; FSH=follicle stimulating hormone; HBV=hepatitis B virus; HCV=hepatitis C virus; HIV=human immunodeficiency virus; IMP=investigational medicinal product; MRI=magnetic resonance imaging; PD=progressive disease; PGIS=Patient Global Impression of Severity; PK=pharmacokinetics; RF=rheumatoid factor; SpO2=Oxygen saturation; TGFβ=transforming growth factor beta; TSH=thyroid stimulating hormone, T4=thyroxine.

Unless stated otherwise in a footnote, all procedures and samples should occur prior to trial drug administration.

- a A time window of up to 3 days before or 1 day after the scheduled visit day (-3 / +1 days) will be permitted for all procedures (except Day 2 and the Day 43-50 visit). The bi-weekly 14-day schedule should be strictly adhered to, returning to the target date even if the previous visit was off schedule. The Day 43-50 visit is to accommodate collection of tumor biopsy material and associated PK and CCI (see Table 3).
- Subjects without progressive disease at End-of-Treatment visit will be followed up for disease progression (CT/MRI scans every 12 weeks) until PD. In addition, subjects will be followed every 12 weeks for survival (including assessment of any further tumor therapy). The survival follow-up will continue until 1 year after the last subject receives the last dose of trial drug. After completion of the Follow-up period, the appropriate electronic Case Report Form section for Trial Termination must be completed.
- c Any subject who experiences an AE that mandates discontinuation of trial treatment should have a discontinuation visit within 7 days after the decision to discontinue trial treatment.
- d Tumor evaluation at the End-of-Treatment visit should only be performed if no disease progression has been documented previously. If another antineoplastic therapy is administered before the end of this 28-day period, the End-of-Treatment visit should be conducted, if possible, prior to the start of this new therapy.
- e Assessments for skin lesions or rash with biopsy of suspicious lesions. Dermatological consults should be requested as needed.
- f ECG to be taken before dosing and as soon as possible after completion of the infusion. If only a single "X", then only ECG before dosing is required. All ECGs will be conducted according to local procedure and will NOT be digitally uploaded.
- Vital signs should be assessed predose (within 15 minutes of start of infusion), then every 15 (±2) minutes after the start of infusion, and 15 (±5), 30 (±5), 60 (±5), 120 (±10), and 360 (±150) minutes after the end of infusion for the first 2 infusions. If there were no clinically significant changes in vital signs during the first 2 infusions, then the vital signs schedule for subsequent infusions will be predose (within 15 minutes of start of infusion), 30 (±5) and 60 (-5/+15) minutes after the start of infusion. For re-initiated subjects, vital signs should be assessed predose (within 15 minutes of start of the infusion), 30 (±5) and 60 (-5/+15) minutes after the start of infusion, and 30 (±5), 60 (±10), and 120 minutes after the end of the infusion. If the re-initiated subject does not have an infusion-related reaction during the first infusion the vital sign assessments at 30 (±5), 60 (±10), and 120 minutes after the end of the infusion may be waived for subsequent infusions.
- h If the Screening ECOG PS was performed within 3 days prior to Cycle 1 Day 1, it does not have to be repeated at Cycle 1 Day 1.

- i Enrollment will be done after the confirmation of fulfilling all Screening inclusion criteria without matching any exclusion criterion. In the case of new clinical laboratory abnormalities detected prior to the first dose, the eligibility of the subject should be reconsidered with the guidance of Medical Monitor.
- j Hematology (including complete blood count) and hemostaseology assessments are detailed in Table 8. Follicle-stimulating hormone at Screening, if applicable. Complete blood count results must also be drawn and reviewed within 48 hours prior to dose administration according to the schedule in the above table. For subjects experiencing signs of anemia including, but not limited to, a significant drop in Hgb value (especially Hgb < 8 g/dL), routine monitoring of Hgb, red blood cells, and hematocrit should be performed weekly.
- k Full chemistry (which includes core chemistry) and core serum chemistry samples are detailed in Table 8. Samples for core chemistry results must be drawn and reviewed within 48 hours prior to dose administration according to the schedule in the above table.
- 1 A full urinalysis is required at Screening and the End-of-Treatment visit and basic urinalysis at each visit indicated prior to administration of trial drug. If urinalysis (full or basic) is positive for protein, sediment will be evaluated.
- m β-HCG must be determined from serum at Screening and from either urine or serum sample thereafter. Results of the most recent pregnancy test should be available prior to next dosing. Pregnancy testing is applied for women of childbearing potential. Woman are considered of childbearing potential unless they are postmenopausal (defined by continuous amenorrhea excluding the amenorrhea caused by the administration of anticancer therapy) for at least 12 months, are surgically sterile or have increased FSH levels

Serum VCA-IgG Ab and EBNA IgG examination should be done for gastric cancer cohort.

In order to mitigate potential infusion-related reactions, all subjects must receive premedication with an antihistamine and with paracetamol (acetaminophen) approximately 30 to 60 minutes prior to each dose of MSB0011359C (eg, 25-50 mg diphenhydramine and 500-650 mg paracetamol [acetaminophen] intravenous or oral equivalent) for the first 2 infusions. Premedication is optional and at the discretion of the Investigator after the second infusion. If Grade 2 infusion reactions are seen during the first two infusions, then premedication should not be stopped. Steroids as premedication are not permitted. MSB0011359C should be administered according to the dose decided from the dose escalation part of the trial by intravenous infusion over 1 hour (-10 minutes/+20 minutes, ie, over 50 to 80 minutes).

- s At each visit, eye signs and symptoms should be checked. If clinically relevant findings, then an appropriate ophthalmology examination including slit lamp evaluation inclusive of the anterior segment and with visual acuity should be obtained within 2 days.
- t After 6 months, this will be assessed every 12 weeks and after a year, this will be assessed every 6 months.
- u After Day 1, the physical examination will be a directed physical examination indicated by subject's symptoms.
- w See Section 7.4.1.3 for definition of the AE reporting period and Section 7.4.1.6 for monitoring of subjects with AEs.
- x Subjects who re-initiate treatment will continue in the trial and will be treated and monitored according to the Schedule of Assessments for the expansion part of the trial starting at Week 1, Day 1.
- y Patient-reported outcomes should be completed prior to any study-related procedures at the indicated visits.
- z For subjects in the GC expansion cohort only, symptom severity also will be assessed using the EORTC QLQ-STO22, stomach cancer module.
- aa For subjects in the ESCC expansion cohort only, symptom severity also will be assessed using the EORTC QLQ-OES18, esophageal cancer module.
- bb For subjects in the BTC expansion cohort only, symptom severity also will be assessed using the EORTC QLQ-BIL21 (cholangiocarcinoma and gallbladder cancer module) and the EORTC QLQ-HCC18 (hepatocellular carcinoma module).

Table 3 Scho	edule of As	ssessi	ment	s – Pl	harm	acok	ineti	cs Sa	mplii	ng, C	CI					
	Screening Assessments	5						tment i / +1 da						Discontinuation/ End-of- Treatment Visits	Safety Follow-up Visit	Long-term Follow-up
	Day -28 to First	W1	V2 W1	V3 W2	V4 W3	V5 W4	V6 W5	V7 W7	V7 W7 D43-	V8 W9	V9 W11	V10 W13	Until	Up to 7/28 Days (±5 days) after Decision of Discontinuation/	10 Weeks (±2 weeks) after Last	Every 12 Weeks
Measure	Treatment	D1	D2 ^{b,l}	D8 ^l	D15	D22 ¹	D29	D43	50 ¹	D57	D71	D85		Last Treatment ^c	Treatment	(±2 weeks)
Dose Escalation																
PK sampling ^{d,e}		X/X/ Xd	Xb	X	X/X/ Xe		X/X/ Xe	X/X/ Xe	Xf	Xe	Xe	Xe	6-weekly up to/including		X	
ADA sampling (HAHA on the CRF) ^g	X				X		X	X		X	X	X	Week 25, then every 12 weeks	- /X	X	
Soluble factorsh		X	Xb	X	X			X				X		- /X		
TGFβ ^h		X	Xb	X	X			X				X		- /X		
CCI																
Expansion: HCC ^m																
PK sampling ^{d, e}		X/X/ X ^d	Xb	X	X/X/ Xe		X	X/X/ Xe	X ^f			X/X/ Xe	6-weekly up to/including Week 25, then every 12 weeks	- /X	X	
ADA sampling (HAHA on the CRF)	X				X		X	X				X	6-weekly up to/including Week 25, then every 12 weeks	- /X	Х	
Soluble factors		X	Xb	Х	X			X				Х	6-weekly up to/including Week 25, then every 12 weeks	- /X		

Table 3 Sche	edule of As	ssessi	ment	s – Pl	harm	acok	ineti	cs Sa	mplii	ıg, C	CI					
	Screening Assessments							tment : / +1 da						Discontinuation/ End-of- Treatment Visits	Safety Follow-up Visit	Long-term Follow-up
		V1 ¹	V2	V3	V4	V5	V6	V7	V 7	V8	V9	V10		Up to 7/28 Days	40 777 1	
	Day -28 to	W1	W1	W2	W3	W4	W5	W7	W 7	W9	W11	W13		(±5 days) after Decision of	10 Weeks (±2 weeks)	Every
Measure	First Treatment	D1	D2 ^{b,l}	D8 ^l	D15	D22 ¹	D29	D43	D43- 50 ¹	D57	D71	D85	Until Progression	Discontinuation/ Last Treatment ^c	after Last Treatment	12 Weeks (±2 weeks)
TGFβ		X	X^b	X	X			X				X		- /X		
Viral load testing (HBV, HCV) ⁿ	X	X			X			X				X	6-weekly up to/including Week 25, then every 12 weeks	- /X	Х	
Alpha-fetoprotein		X			X			X				X	6-weekly up to/including Week 25, then every 12 weeks	- /X		
CCI																
Expansion: GC, ESCC and BT	C															
PK sampling ^{d, e}		X/X/ X ^d	Xb	X	X/X/ Xe		X	X/X/ Xe	X ^f			X/X/ Xe	6-weekly up to/including Week 25, then every 12 week	- /X	X	
ADA sampling (HAHA on the CRF) ^g	X				X		X	X				X	6-weekly up to/including Week 25, then every 12 weeks	- /X	Х	

Table 3 Scho	Table 3 Schedule of Assessments – Pharmacokinetics Sampling, CCI															
	Screening Assessments	Treatment Phase												Discontinuation/ End-of- Treatment Visits	Safety Follow-up Visit	Long-term Follow-up
Measure	Day -28 to First Treatment	V1 ^l	V2	V3	V4	V5	V6	V7	V7	V8	V9	V10		Up to 7/28 Days (±5 days) after Decision of Discontinuation/ Last Treatment ^c	10 Weeks (±2 weeks) after Last	
		W1 D1	W1 D2 ^{b,l}	W2 D8 ^l	W3 D15	W4 D22 ¹	W5 D29	W7	W7 D43- 50 ¹	W9 D57	W11					Every 12 Weeks (±2 weeks)
Soluble factors		X	Xb	X	X			X				X	6-weekly up to/including Week 25, then every 12 weeks			
TGFβ		X														
CCI															_	

ADA=anti-drug antibody; BTC=biliary tract cancer; CRF=case report form; ESCC=esophageal squamous cell carcinoma; GC=gastric cancer; HAHA=human antibudy; HBV=hepatitis B virus; HCC=hepatocellular carcinoma; HCV=hepatitis C virus; PD=progressive disease; PK=pharmacokinetics; TGFβ=transforming growth factor beta.

Unless stated otherwise in a footnote, all procedures and samples should occur prior to trial drug administration.

- a A time window of up to 3 days before or 1 day after the scheduled visit day (-3 / +1 days) will be permitted for all procedures (except Day 2 and the Day 43-50 visit). The bi-weekly 14-day schedule should be strictly adhered to, returning to the target date even if the previous visit was off schedule.
- b The Day 2 PK and contained a samples must be drawn at least 24 hours after the Day 1 end of infusion, preferably > 30 hours after end of infusion. The exact time of each draw must be recorded. A protocol deviation will be defined by a sample not being drawn or by a predose sample being drawn after start of dosing.
- c If another antineoplastic therapy is administered before the end of this 28-day period, the End-of-Treatment visit should be conducted, if possible, prior to the start of this new therapy.
- d Blood samples for PK analysis should be drawn on Day 1 prior to dosing, immediately after completion of the infusion, and 4 hours after the start of the infusion.
- e Samples for PK analysis to be taken before infusion (as close to the start of the infusion as possible), immediately after the completion of infusion, and 2 to 8 hours after the end of infusion (the later the better). If only 1 blood sample is scheduled at a visit, this is to be taken prior to the IMP administration. The exact time of each draw must be recorded. A protocol deviation will be defined by a sample not being drawn.
- f A PK sample should be collected as close as possible to the time of mandatory/optional Week 7 biopsy as possible (ie, same day).
 - An ADA sample should be taken prior to infusion, and the actual time of sample collection should be recorded.

CCI

Subjects who re-initiate treatment will continue in the trial and will be treated and monitored according to the Schedule of Assessments for the expansion part of the trial starting at Week 1, Day 1.

- m No re-initiated HCC subjects as all completed/discontinued study.
- n Subjects who are HBV positive should be tested for HBV viral load assessed according to the HCC schedule. Subjects with a previous history of HCV infection who have sustained viral response should have HCV viral load assessed at the Investigator's discretion according to the HCC schedule. Subjects who are HCV antibody positive at Screening should have HCV viral load assessed according to the HCC schedule.

2 Sponsor, Investigators and Trial Administrative Structure

The Sponsor of this clinical trial with MSB0011359C is Merck Biopharma Co., Ltd. (affiliate of Merck KGaA, Darmstadt, Germany) in Japan. In addition, Merck KGaA, Darmstadt, Germany, sponsors this clinical trial in Korea and Taiwan.

Trial Organization in Japan

Refer to the Trial Organization in Japan supporting document.

PPD

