	Day -28 to	D1	D2	D8	D15	D22	D29	D43	D43-50	D57	D71	D85]	Discontinuation/	(+/- 2 weeks)	
Measure	First Treatment												Until Progression	Last Treatment	after Last Treatment	Every 12 weeks (+/- 2 weeks)
Tumor evaluation/ staging (CT Scan/MRI/ other) ^{b, n, o, v}	X							Х				X	6-weekly	-/X		X _p
Documentation of AEsw	X	X	X	X	X	X	X	X	X	X	X	X	2-weekly	x/X ^w	Xw	
Documentation of concomitant medications, and procedures	X	X	X	X	X	X	X	Х	X	X	X	X	2-weekly	x/X	Х	X
ACTH, ANA, and RF	X															
Free T4 and TSH	X				X			X				X	6-weekly	-/X	X	
PK sampling										See	Table	3				
ADA sampling										See	Table	3				
Soluble factors										See	Table	3				
TGFβ										See	Table	3				
Tumor tissue or archived surgical specimen (optional)										See	Table	3				
CCI						_				CC						
CCI	C															
Pretreatment and IMP administration ^q		X			X		X	X		X	X	X	2-weekly			

Table 1	Schedul	e of .	Asse	ssme	ents:	Dos	e Es	calat	ion Pa	rt						
	Screening Assessments								ent Part days) ^a					Discontinuation/ End-of- Treatment Visits ^w	Safety Follow-up Visit ^w	Long-Term Follow-up ^b
		V1	V2	V3	V4	V5	V6	V7	V7	V8	V9	V10		Up to 7/28 Days		
		W1	W1	W2	W3	W4	W5	W 7	W7	W9	W11	W13		(+/- 5 days) after Decision of	10 Weeks	
	Day -28 to	D 1	D2	D8	D15	D22	D29	D43	D43-50	D57	D71	D85		Discontinuation/	(+/- 2 weeks)	
Measure	First Treatment												Until Progression	Last Treatment	after Last Treatment	Every 12 weeks (+/- 2 weeks)
Hospitalization on first 2 doses ^r		X			X											
DLT assessment ^s		X	X	X	X	X										
Survival follow-up																X

ACTH=adrenocorticotropic hormone; ADA=anti-drug antibody; AE=adverse events; ANA=antinuclear antibody; β -HCG= β -human chorionic gonadotropin; CT=computer tomography; DLT=dose-limiting toxicity; ECG=electrocardiogram; ECOG PS=Eastern Cooperative Oncology Group Performance Status; FSH=follicle stimulating hormone; HBV=hepatitis B virus; HCV=hepatitis C virus; HIV=human immunodeficiency virus; IMP=investigational medicinal product; MRI=magnetic resonance imaging; PD=progressive disease; PK=pharmacokinetics; RF=rheumatoid factor; SpO₂=Oxygen saturation; TGF β =transforming growth factor beta; TSH=thyroid stimulating hormone, T4=thyroxine.

Unless stated otherwise in a footnote, all procedures and samples should occur prior to trial drug administration.

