- a A time window of up to 3 days before or 1 day after the scheduled visit day (-3/+1 days) will be permitted for all procedures (except Day 2 and the Day 43-50 visit). The biweekly 14-day schedule should be strictly adhered to, returning to the target date even if the previous visit was off schedule. The Day 43-50 visit is to accommodate collection of tumor biopsy material and associated PK and CCI (see Table 3).
- b Subjects without progressive disease at End-of-Treatment visit will be followed up for disease progression (CT/MRI scans every 12 weeks) until PD. In addition, subjects will be followed every 12 weeks for survival (including assessment of any further tumor therapy). The survival follow-up will continue until 1 year after the last subject receives the last dose of trial drug. After completion of the Follow-up period the appropriate electronic Case Report Form section for Trial Termination must be completed.
- c Any subject who experiences an AE that mandates discontinuation of trial treatment should have a discontinuation visit within 7 days after the decision to discontinue trial treatment.
- d Tumor evaluation at the End-of-Treatment visit should only be performed if no disease progression has been documented previously. If another antineoplastic therapy is administered before the end of the 28-day period, the End-of-Treatment visit should be conducted before the start of new therapy if possible.
- e Assessments for skin lesions or rash with biopsy of suspicious lesions. Dermatological consults should be requested as needed.
- f ECG to be taken before dosing and as soon as possible after completion of the infusion. If only a single "X", then only ECG before dosing is required. All ECGs will be conducted according to local procedure and will NOT be digitally uploaded.
- Wital signs should be assessed predose (within 15 minutes of start of infusion), then every 15 (±2) minutes after the start of infusion, and 15 (±5), 30 (±5), 60 (±5), 120 (±10), and 360 (±150) minutes after the end of infusion for the first 2 infusions. If there were no clinically significant changes in vital signs during the first 2 infusions, then the vital signs schedule for subsequent infusions will be predose (within 15 minutes of start of infusion), 30 (±5) and 60 (-5/+15) minutes after the start of infusion, and 30 (±5), 60 (±10), 6

28/167

Global Version ID: CC

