- n Tumor evaluations during Screening must be performed within 28 days prior to Cycle 1 Day 1 in order to document the baseline status of the tumor disease using RECIST 1.1 target and nontarget lesions. The subsequent tumor evaluations have a time window of 5 days prior to dosing (-5 days). In case a tumor response according to RECIST 1.1 is documented during the course of the trial, confirmation of the response should be performed according to RECIST 1.1 after 6 weeks.
- o Brain CT/MRI scan (either, with contrast preferred) is required at Screening if not performed within the previous 6 weeks. Thereafter, brain CT/MRI scan should be done if clinically indicated by development of new specific symptoms. A bone scan should be done at Screening and beyond as clinically indicated. Bone metastases detected at Screening need to be followed at the subsequent tumor evaluation visits.
 - In order to mitigate potential infusion-related reactions, all subjects must receive premedication with an antihistamine and with paracetamol (acetaminophen) approximately 30 to 60 minutes prior to each dose of MSB0011359C (eg, 25-50 mg diphenhydramine and 500-650 mg paracetamol [acetaminophen] intravenous or oral equivalent) for the first 2 infusions. Premedication is optional and at the discretion of the Investigator after the second infusion. If Grade 2 infusion reactions are seen during the first two infusions, then premedication should not be stopped. Steroids as premedication are not permitted. MSB0011359C should be administered at the cohort prescribed dose by intravenous infusion over 1 hour (-10 minutes/+20 minutes, ie, over 50 to 80 minutes). The first 2 doses of MSB0011359C for any subject will be accompanied by overnight evaluation of at least 24 hours in an in-patient setting.
- r In-patient admission with periodic ECG and vital sign monitoring for a minimum of 24 hours. After 24 hours, investigator will decide the discharge of the subject based on the monitoring results and the results of in-person examination.
- s The observation period for DLTs refers to the first 21 days of IMP treatment in the dose escalation part for all subjects with data used for implementing the dose-escalation algorithm for determination of the MTD.

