5.1.3.2 Dose Escalation

The dose escalation will use a standard 3+3 scheme with the following planned doses:

- 3 mg/kg
- 10 mg/kg
- 20 mg/kg

The DLT period is defined as 21 days after the start of therapy. The first subject of each cohort will be observed for at least 5 days before the second subject can be treated. Thereafter, within each cohort, 48 hours must pass before a new subject can initiate dosing. Once the 3 or 6 subjects have passed the 21-day DLT evaluation period, the SMC will review the safety and available PK data to decide upon further dose escalation. Pharmacokinetics data from the previous cohort will be required for SMC review (eg, when the SMC is reviewing safety data from the 10 mg/kg cohort, available PK data from the 3 mg/kg cohort); however, PK data from the cohort under review will not be required).

For each dose level, DLTs are assessed during the first 3 weeks (Figure 1). The criteria for moving from one dose level to another do not allow escalation to the next cohort in cases where more than 1 subject in a cohort experience a DLT. If 1 of 3 subjects in a cohort experiences a DLT, this cohort will be expanded to 6 subjects with the SMC meeting after the 6th subject completes the DLT evaluation period.

The MTD is defined as the highest dose where no more than 1 subject out of 6 subjects experiences a DLT. Thus, the MTD cohort should accrue a total of 6 subjects (Figure 2).

After completion of the DLT evaluation at 3 and 10 mg/kg in the dose escalation part, enrollment in the HCC expansion cohort will start at 3 and 10 mg/kg, respectively.

After determination of the MTD in the dose escalation part, an MSB0011359C dose for further investigation will be selected and enrollment in the expansion cohorts of subjects with GC, ESCC, and BTC will begin (Figure 1).

The DLT criteria will not apply to any of the expansion cohorts.

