7.1.2 Treatment Period

For this protocol, a cycle is defined as 14 days. In this trial, the treatment will be given until confirmed progression, unacceptable toxicity, or any criterion for withdrawal from the trial or IMP occurs (see Section 5.5). Subjects who have experienced a CR, PR or SD should continue treatment through the end of 12 months after confirmation, although additional treatment is possible. If the Investigator believes that a subject may benefit from treatment beyond 12 months, it may be permissible after discussion with the Medical Monitor. In the case of PD, subjects should continue treatment through their next tumor assessment, if they meet the criteria described in Section 5.5.1.

1

For subjects who achieve CR, PR, or SD on MSB0011359C therapy and then subsequently develop disease progression after stopping therapy, but prior to the end of the trial, 1 re-initiation course of treatment at the same dose and schedule and treatment duration up to 12 months is allowed at the discretion of the Investigator and agreement of the trial Medical Monitor. In order to be eligible for retreatment, the subject must not have experienced any toxicity that led to treatment discontinuation of the initial MSB0011359C therapy. Prior to re-initiation of the trial treatment, malignant disease needs to be radiologically re-staged to assess all known sites of the disease and to establish a new baseline for subsequent tumor measurements. Relevant safety laboratory samples must be drawn and results available and verified prior to re-initiating of treatment. Subjects who re-initiate treatment will stay on trial and will be treated and monitored according to the Schedule of Assessments for the expansion part of the trial (see Table 2).

Subjects will be asked to visit the investigational site according to the Schedules of Assessments (see Table 1 and Table 2). A time window of up to 3 days before or 1 day after the scheduled visit day (-3/+1 days) will be permitted for all trial procedures (except on Day 2 and the Day 43 to 50 visit). In addition, the tumor evaluation (see Section 7.3) has a tumor assessment visiting time window of 5 days prior to dosing (-5 days). Furthermore, if any Screening procedures are conducted within 3 days prior to Day 1 of trial treatment (Week 1, Day 1), the assessments scheduled on Week 1, Day 1 do not need to be repeated except for the evaluation of AEs and concomitant medications.

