9.3 Treatment Day

Treatment day is defined relative to the start of trial treatment. Treatment day 1 is defined as the date of first administration of trial treatment. The day before the first administration of trial treatment is defined as Treatment day -1 (there is no Treatment day 0).

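### The visit window lets the Day 22 DLT assessment and safety labs fall on Day 19, 2 to 3 days before the 21-day DLT period ends, and no later check is required before SMC review

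*Protocol*

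**What the plan says.** Protocol Table 1 (dose escalation) has a row "DLT assessment" marked at Days 1, 2, 8, 15 and 22. Day 22 also carries a physical examination, vital signs, hematology and core serum chemistry. Protocol Table 8 places ALT, AST and bilirubin in the core panel. The next visit is Day 29.

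Footnote a to Table 1 lets visits move from three days early to one day late; from the figure onward it reads "3/+1 days) will be permitted for all procedures (except Day 2 and the Day 43-50 visit". Section 7.1.2 repeats the rule: "will be permitted for all trial procedures (except on Day 2 and the Day 43 to 50 visit". Neither place excepts Day 22.

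The DLT period is stated in two ways. Section 5.1.3.2: "The DLT period is defined as 21 days after the start of therapy". Table 1, footnote s: "The observation period for DLTs refers to the first 21 days of IMP treatment in the dose escalation part". SAP Section 9.3 fixes the day count: "Treatment day 1 is defined as the date of first administration of trial treatment".

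On the escalation decision, Section 5.1.3.2 says: "Once the 3 or 6 subjects have passed the 21-day DLT evaluation period, the SMC will review the safety and available PK data". If a cohort is expanded to six, the review comes "with the SMC meeting after the 6th subject completes the DLT evaluation period".

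**The concern.** Day 22 is the only scheduled DLT assessment that falls after 21 days of treatment, so it closes the period. Other visits whose timing matters (Day 2, Day 43-50) are taken out of the general window, but this one is not. If it is held on Day 19, the last 2 to 3 days of the period have no scheduled examination or laboratory sample until the Day 29 visit.

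The SMC needs only that the subjects have passed 21 days. The documents provided do not require a contact or blood draw at or after that point. The DLT analysis set (Section 8.4) depends on treatment received or on stopping for a DLT, not on a closing assessment. The replacement rules (Sections 5.5.1 and 5.5.2) do not name an early closing visit. A subject last seen on Day 19 with no event can therefore count as DLT-free.

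Occurrence of DLTs over 21 days is the first primary endpoint for escalation. It drives dose escalation, the MTD, and the opening of the HCC and other expansion cohorts. Some DLT criteria in Section 5.1.3.3 are laboratory findings, notably ALT or AST at 3 times ULN with bilirubin at 2 times ULN, and these may be seen only if blood is drawn.

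**Working it through.** **Inputs.** Visit days and window: Protocol Table 1, footnote a, and Section 7.1.2. DLT period: Section 5.1.3.2 and footnote s. Day 1 is the first dose: SAP Section 9.3. Decision rule and spacing of subjects: Section 5.1.3.2.

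**1. The plan's own figure.** Day 1 + 21 = Day 22. The nominal visit day agrees with the 21-day period.

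**2. Permitted range of the Day 22 visit.** 22 − 3 = Day 19; 22 + 1 = Day 23. That is 18 to 22 days after the first dose. SAP Table 1 assigns Days 19 to 25 to Week 4 Day 22, so by-visit laboratory and vital-sign tables would not show an early visit.

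**3. Days without a scheduled assessment after a Day 19 visit.**
- Period read as Days 1 to 21: 21 − 19 = 2 days; 2/21 = 9.5%.
- Period read as 21 days after Day 1: 22 − 19 = 3 days; 3/21 = 14.3%.

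**4. Next scheduled visit.** 29 − 3 = Day 26 to 29 + 1 = Day 30. Pre-dose blood may be drawn up to 48 hours before dosing, so Day 24 at the earliest (26 − 2). All of this is after the period has ended, and SMC review is not made to wait for it.

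**5. Time from second dose to closing visit.** Nominal: 22 − 15 = 7 days. With both windows at their extremes: 19 − 16 = 3 days.

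**6. Who is affected at the earliest SMC review.** Subject 2 starts at least 5 days after subject 1, and subject 3 at least 48 hours after subject 2. When subject 3 reaches Day 22, subject 2 is at Day 24 or later (22 + 2) and subject 1 at Day 29 or later (22 + 2 + 5). The gap therefore concerns mainly the last one or two subjects of a cohort.

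**7. When one event changes the decision.** 0/3 to 1/3: escalate becomes expand to six. 1/6 to 2/6: acceptable becomes not acceptable. 0/6 to 1/6: no change, because the MTD rule tolerates one in six.

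**8. Illustration, on assumptions not in the documents.** DLT risk is spread evenly over the period, every subject is seen on Day 19, and every later DLT is missed. With DLT probability p, P(escalate) = (1−p)³ + 3p(1−p)² × (1−p)³. The visible probability becomes p × 19/21 (2-day gap) or p × 18/21 (3-day gap).

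| True DLT rate | Full period | 2-day gap | 3-day gap |
|---|---|---|---|
| 10% | 0.906 | 0.921 | 0.929 |
| 20% | 0.709 | 0.750 | 0.770 |
| 30% | 0.494 | 0.554 | 0.584 |
| 40% | 0.309 | 0.375 | 0.410 |

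Given even timing, this is an upper bound: adverse events are still collected after Day 19, and step 6 shows that not every subject is exposed to the gap. If DLTs cluster late in the period, the share falling in the gap would exceed 9.5% to 14.3%.

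**The case against.** A reader might infer that the window lets the SMC escalate before the DLT period is over. The documents do not support that. Section 5.1.3.2 ties the review to subjects having passed 21 days, and an early visit changes neither the period nor the date of the review.

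A reader might also infer that the days after a Day 19 visit go unwatched. That is wrong too. Adverse events are recorded continuously (Section 7.4.1.6), DLTs are monitored centrally (Section 5.1.1.1), and a DLT must be entered within 24 hours of awareness (Section 7.4.1.4). Clinically significant new laboratory abnormalities are repeated weekly (Section 7.4.3), and hemoglobin is checked weekly in subjects with signs of anemia (Table 1, footnote j). A problem already visible on Day 19 would be followed.

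Further points limit the concern:
- A Grade 3 hemoglobin decrease is excepted if it recovers within 14 days, so a late drop could not be finally classified on Day 22 either.
- The primary endpoint is not lost. An event that starts in the period but is documented later still counts in the final analysis. Only the real-time decision is exposed.
- Continuing subjects must sign a further consent after the DLT period (Sections 7.1.2.1 and 9.2), and Table 1 places it at Day 22. This links the visit to completion of the period but does not bar holding it early.
- SMC working procedures are in a charter that is not available here (Section 2.2.1). It may require confirmation of DLT status.
- SAP Section 4 gives 24 August 2017 as the start date of the last participant, so no initial DLT period remains to be protected.

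These points narrow the concern considerably. They do not supply a scheduled sample or examination at the end of the period, and continuous reporting cannot detect a silent laboratory change that nobody measures.

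**Conclusion.** The concern holds in a narrow form. The general window and the 21-day definition do not fit together: the closing DLT assessment and labs may precede the end of the period by 2 to 3 days, and nothing in the protocol or SAP requires a later check before SMC review. What is exposed is a new, clinically silent laboratory DLT that arises after an unremarkable Day 19 panel, most likely in the last one or two subjects of a cohort. It matters for the decision at 0/3 or 1/6, not at 0/6. The shifts in step 8 (for example 0.494 to 0.554-0.584 at a true rate of 30%) show the direction, toward escalation, and should not be read as an expected effect. The conclusion assumes that sites use the early side of the window and that the SMC charter adds no confirmation step. It does not support a claim that escalation was allowed before the DLT period had elapsed, or that the DLT endpoint is invalid.

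**What to change.** Reconcile the visit window with the 21-day definition:
- In Table 1, footnote a, and in Section 7.1.2, add the escalation Day 22 visit to the exceptions, so that the closing DLT assessment, hematology and core chemistry do not precede the end of the period. If only the one-day late allowance is kept, the visit falls on Day 22 or 23 and no day of the period is left uncovered.
- In Section 5.1.3.2, state that SMC review follows each subject's closing DLT assessment.
- Use one reading of the period (through Day 21, or through Day 22) in Section 5.1.3.2 and footnote s.

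The cost is a few sentences, slightly less scheduling freedom for up to 18 escalation subjects, and possibly an SMC meeting a few days later. For subjects already treated, the practical step is to list the actual Day 22 visit and sample dates beside the DLT counts and show whether any fell before the period ended.
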